4.5.3 Exploratory Endpoints

The home FVC (ml) absolute decline >10% compared to baseline occurring at least in 3 consecutive days will be presented by study periods. The number of patients with and without a decline and the number of occurrences of a categorical decline will be summarized in each diagnosis cohort. The overall duration of all observed categorical declines per patient (days) will be summarized descriptively.

With respect to the evaluation of the collaboration platform by means of a survey among investigators and the digital solution set up by means of a patient questionnaire, descriptive frequency tables will be prepared at the end of the trial. Please refer to [Appendix 6](#) for further information about the patient survey.

4.5.4 Sensitivity Analyses

The following sensitivity analyses related to be primary endpoint will be presented:

- The time-adjusted semi-annual mean FVC decline (mL) during peri-diagnosis period estimated from good blow quality daily home spirometry measurements excluding measurements with a difference >50% or <50% from baseline site FVC.
- The time-adjusted semi-annual mean FVC decline (mL) during peri-diagnosis period estimated from good blow quality daily home spirometry measurements excluding patients with measurements collected for less than 30 days after baseline.
- The two analyses specified above will be repeated to estimate the semi-annual mean FVC decline during the peri-diagnosis period by a single arm repeated measures mixed model with patient effects and day of measurement fitted as random effects.

In addition, sensitivity analyses to the primary analysis may be performed using a repeated measures mixed model by including additional factors and covariates (e.g. gender, height) into the model.

Additionally, the impact of different assumptions with respect to the variance-covariance matrix underlying the repeated measures mixed model may be investigated.

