2.2.1 Primary Outcome Measures

Throughout the study, patients should perform a spirometry measurement of FVC [mL] at approximately the same time each day. For this purpose, study participants will be provided with a portable handheld spirometer and a tablet computer. Each spirometer will be factory calibrated.

The primary outcome measure is pulmonary function by use of FVC measurements in mL by daily home spirometry.

Note that for every FVC measurement the quality of the manoeuvre is monitored and documented according to acceptability criteria shown in the flow chart of Appendix [3](#). Depending on different characteristics of the blow, quality criteria will be provided to the patient and documented with the measurement (e.g. “blow out faster”, “blow out longer”).

Table 1 shows which of the quality criteria are considered acceptable and not acceptable manoeuvres.

Based on the Steering Committee (SC) feedback and in order to exclude the potential learning curve of each patient, the first 7 days of measurements per patient will be

removed from the analyses. All measurements will be taken into account for the analyses in case we have more than 1 per day.

Table 1 Quality criteria for FVC measurements

Not acceptable manoeuvre	Acceptable manoeuvre

 • Blow out faster • Blow out longer • Abrupt end 	
 • Don't start too early • Avoid coughing • Good blow

For analysis purpose only non-test acceptable manoeuvres flagged as 'Good blow' will be considered. In addition, any data point collected by the device before enrollment visit and after EOS visit, respectively, will be excluded from the analysis. In case a patient received treatment before EOS visit all data after treatment start date (inclusive site spirometry etc.) will be excluded from analysis as well. In order to consider only data points that are clinically meaningful FVC values outside a range from 400 ml to 6000 ml will also be excluded from analysis.

The corresponding primary endpoint used for the investigation of disease behavior of IPF is defined as the time-adjusted semi-annual FVC decline in patients with IPF during the peri-diagnosis period. Please refer to Section [4.5.1](#) for a detailed description of statistical analysis which is used for the computation of the primary endpoint.

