2.2.2.2 Physical function capacity

Patients will be asked to wear an accelerometer during the course of the study which provides information on their physical activity, such as steps per day and calorie expenditure. These daily measurements will be used to investigate the development of physical function capacity over time. The first 7 days of measurements per patient will be removed from the analyses as done with spirometry home data. In addition, any data point collected before enrollment visit up to start of treatment or EOS visit whatever occurred first will be deleted and for steps per day (SPD) a range for acceptable values from 200 to 20000 will be applied.

2.2.2.3 6MWT

The 6MWT measures the distance a patient is able to walk quickly on a flat, hard surface in a period of 6 minutes.

The 6MWT should be conducted at each patient visit, only at sites where a formalized process is available and the test can be performed under safe conditions.

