- Change in physical functional capacity (measured by daily home accelerometry, e.g. number of footsteps per day) from baseline over time for each diagnosis cohort
- Change in PRO measures from enrollment visit to diagnosis visit and EOS visit as well as change from diagnosis visit to EOS visit over time will be summarized for each diagnosis cohort.

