4.2.4 Post-diagnosis Assessment Period

Patients diagnosed with IPF or non-IPF ILD at Visit 2 will remain and be followed in the study up to the start of drug treatment (within 6 months) or a maximum of 6 months if no drug treatment is prescribed.

“Start of drug treatment” is defined as the date the treatment is planned to commence. This includes the event of a patient receiving IPF or ILD drug treatment from a physician other than the investigator.

The length of the post-diagnosis period is thus defined as:

Post-diagnosis period = date of start of drug treatment – date of initial diagnosis or
= date of end of study visit – date of initial diagnosis

whichever comes first, where diagnosis date is taken from the IPF/ILD diagnosis eCRF page. In addition, any data point collected after initiation of treatment until EOS visit will be excluded from any analysis.

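### Two home-data exclusion rules are wrong as worded: the steps/day sentence deletes the on-study window, and the 50% FVC limit excludes almost every reading (minor; intent recoverable)

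*SAP*

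**What the plan says.** **Steps per day (SAP 2.2.2.2).** Daily accelerometry is to show how physical function develops over time. Three data rules follow:

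- A run-in rule: "The first 7 days of measurements per patient will be removed from the analyses as done with spirometry home data".
- A window rule: "any data point collected before enrollment visit up to start of treatment or EOS visit whatever occurred first will be deleted".
- A plausibility rule for steps per day: "a range for acceptable values from 200 to 20000 will be applied".

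**The parallel windows.** For home spirometry, section 2.2.1 says that "any data point collected by the device before enrollment visit and after EOS visit, respectively, will be excluded from the analysis", and it also drops data after the treatment start date. Section 4.2.4 adds a general rule: "any data point collected after initiation of treatment until EOS visit will be excluded from any analysis".

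**Home FVC sensitivity analysis (SAP 4.5.4).** The first listed analysis repeats the primary estimate on good-quality home blows, "excluding measurements with a difference >50% or <50% from baseline site FVC". The second leaves out patients with under 30 days of measurements after baseline. A third bullet carries both forward to a mixed model: "The two analyses specified above will be repeated to estimate the semi-annual mean FVC decline during the peri-diagnosis period". No other section restates the 50% limit.

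**The concern.** Both sentences are operative instructions that decide which records enter an analysis. Taken at their word, each removes the data that the analysis needs.

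For steps per day, the deleted stretch runs from before enrollment to the earlier of treatment start and the end-of-study (EOS) visit, which is the time the patient is under observation. The affected outputs include the change in physical functional capacity (endpoint list closing section 2.2.2.4), baseline steps per day (4.4.3.1), the individual step graphs and the correlation with walk distance (4.5.2), and the steps part of the progressor definition (4.4.3.3).

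For FVC, a condition met both above and below the same number excludes everything except the number itself. What is at stake there is one supportive analysis and its mixed-model repeat.

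In both places the programmer must replace the written rule with an inferred one. Sections 4.2.2 and 4.9 show that the current text was written after the first interim analysis had been reviewed, so it is better that the limits stand in the plan than that they are settled in programming.

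**Working it through.** The plan attaches no figure to either rule, so there is none to reproduce. The check applies each sentence as written.

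**1. Steps window**

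Let E be the enrollment visit, T the treatment start and S the EOS visit.

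- Section 2.2.2.2 as written deletes every day up to min(T, S). What remains is dated after min(T, S).
- If T comes before S, section 4.2.4 removes the days after T up to S. What remains is dated after S.
- Section 4.2 ends the peri-diagnosis period at the EOS visit, and section 4.5 analyses daily data only within the peri-, pre- and post-diagnosis periods. Nothing usable is left.

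Illustrative timeline (assumed): E = day 1, T = day 200, S = day 230.

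| Rule | Days 1 to 200 kept |
|---|---|
| As written | 0 of 200 |
| Delete before E and after min(T, S) | 200 of 200, before the 7-day and 200–20000 filters |

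The other two rules in 2.2.2.2 confirm the intent. Trimming 7 days and applying a plausibility range have no purpose if every on-study day has already gone. The home baseline in section 4.2.2, a 7-day average following the removed days, also lies inside the deleted window.

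**2. FVC limit**

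Let B be the baseline site FVC (enrollment visit, section 4.2.2), x a home reading, and d = 100 × (x − B) / B.

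- As written: exclude if d > 50 or d < 50. A reading is kept only if d = 50, that is x = 1.5B. If the difference is taken as absolute, x = 0.5B is also kept.
- Two-sided reading: exclude if d > 50 or d < −50. A reading is kept if 0.5B ≤ x ≤ 1.5B.

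Example with B = 2500 mL (assumed) over every whole mL in the 400 to 6000 mL range that section 2.2.1 allows:

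- Possible values: 6000 − 400 + 1 = 5601.
- Kept as written: 1 value (3750 mL), or 2 values (1250 and 3750 mL) with an absolute difference.
- Kept under the two-sided reading: 1250 to 3750 mL.

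A simulation used B = 1500, 2500 and 3500 mL, home-to-site SD of 10, 20 and 30%, bias of −10, 0 and +10%, and 10 mL resolution. All of these are assumptions; the SAP gives none of them.

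| Home-to-site SD | Excluded as written | Excluded, two-sided |
|---|---|---|
| 10% | about 100% | about 0% |
| 20% | 99.8–100% | 1.2–2.4% |
| 30% | 99.5–99.9% | 8.5–11.3% |

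**3. Reach**

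Section 4.5.4 lists two analyses by two methods, 2 × 2 = 4 runs. The 50% rule enters two of them. The other two use the 30-day rule and are untouched, as is the primary analysis in section 4.5.1.

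**The case against.** The strongest reply is that nobody would run either rule literally. An outlier screen cannot be meant to keep only readings exactly 50% away. The sensible forms of the FVC limit also coincide: a difference above +50% or below −50% selects the same readings as a value above 150% or below 50% of baseline. For steps, sections 2.2.1, 4.2.4 and 4.5 together fix the window. This stands as an argument about severity. It does not make the written rules right.

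A second reply is that a minus sign may have been lost when the PDF was read. That is possible for 4.5.4, although minus signs survive in the date formulas of sections 4.2.1 and 4.2.3. It cannot explain 2.2.2.2, which is written in words.

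Two stronger readings are tempting and unsupported:

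- A reader might infer that the FVC rule leaves every patient with too few readings for a slope. The SAP gives no device resolution, and section 2.2.1 keeps all readings when there are several a day. At 10 mL resolution, with B = 1500 mL, SD 30%, no bias and an absolute difference, about 0.45% of readings survive; 0.0045 × 548 days (the 18-month maximum at one reading a day) is about 2.5 readings. Almost no data is established; a firm per-patient ceiling is not.
- A reader might infer that the progressor classification collapses. Section 4.4.3.3 joins its criteria with and/or, so the FVC criterion still works without steps.

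**Conclusion.** Both sentences are wrong as written, and the point is minor. The steps/day sentence is the firmer one: read literally it leaves no on-study accelerometry data, and this conclusion needs no numerical assumption. The FVC sentence leaves almost no data for one sensitivity analysis and its mixed-model repeat. That follows from the logic of the two inequalities; the simulated percentages only illustrate it and rest on assumed baselines, variability, bias and resolution. The FVC part is also conditional on the sentence having been read correctly from the PDF.

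The intended steps window is confirmed by other sections. The intended FVC limit has one sensible reading, but it is inferred, because no other section states it. The documents do not support any claim that the primary result or the 30-day analyses are affected, nor that reported steps/day results would in fact be empty.

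**What to change.** Reword two sentences.

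- Section 2.2.2.2: delete accelerometry data points dated before the enrollment visit, and those dated after the earlier of treatment start and the EOS visit. This agrees with sections 2.2.1 and 4.2.4.
- Section 4.5.4: exclude home measurements for which |home FVC − baseline site FVC| / baseline site FVC > 50%. First check the source file for a minus sign; the absolute-value form removes the doubt either way.

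The cost is two sentences of SAP text. No new data are needed and the primary analysis does not change.

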4.2.2 Baseline Observations

After discussion of the results of the first interim analysis from December 2018 with the SC in January 2019 it was decided to re-define the calculation for baseline FVC from home spirometry and steps per day from accelerometry. This new definition is given in Table 2 below.

Table 2 Definition of Baseline Observations

	Definition
Baseline data for site visit measurements	Baseline is defined as the measurement collected at the enrollment visit of each assessment.
Baseline data for home measurements	Baseline is defined as the average of the daily measurements collected during the next 7 consecutive days after the first 7 days removed, counted from the day of the first acceptable manoeuvre flagged as 'Good blow' of home spirometry after enrollment visit as defined in Table 1.

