4.5.1 Primary Endpoints

The primary endpoint of the study is the time-adjusted semi-annual mean FVC decline (mL) in patients with IPF during the peri-diagnosis period (see Section 4.2) estimated from daily home spirometry measurements.

The semi-annual mean FVC decline is calculated by use of the estimated semi-annual FVC decline of each individual patient. The individual FVC decline is thereby estimated by applying a linear regression model to all acceptable FVC measurements flagged as 'Good blow' according to the MIR criteria (please refer to Section 2.2.1 for the definition of acceptable measurements) collected by the individual patient during the entire peri-diagnosis period, i.e.

$$X_{it} = \alpha_i + \beta_i D_{it} + u_{it}$$

where

X_{it} = the FVC measurements (mL) of patient i on day t , with $i=1, \dots, N$ and $t=1, \dots, T$

D_{it} = study day t of patient i

α_i, β_i = intercept and slope of the individual linear regression of patient i

The time-adjusted semi-annual decline for patient i is then obtained by estimating the patients' individual difference in predicted values between baseline (study day 0) and study day 183 from the linear regression:

$$\widehat{\Delta X}_{i,183} = \widehat{\beta}_i * 183$$

In a further step, the time-adjusted semi-annual mean FVC decline is estimated by calculating the mean over all individual time-adjusted semi-annual declines of all IPF patients.

A summary table displaying the semi-annual mean FVC decline during the peri-diagnosis period together with two-sided 95% confidence intervals based on percentiles of the t-distribution will be provided for IPF patients (primary analysis) and non-IPF ILD patients (secondary analysis). The same table is also provided for patients of all diagnosis cohorts for the pre-diagnosis period at 3, 6 and 12 months.

Further sensitivity analyses are specified under [Section 4.5.4](#).

A table displaying parameter estimates for the different diagnosis cohorts together with 95% confidence intervals and expected semi-annual and annual FVC values will be provided.

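### Does the mixed-model sensitivity analysis in SAP Section 4.5.4 leave the semi-annual mean FVC decline undefined because no fixed day slope is named?

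*SAP*

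**What the plan says.** Section 4.5.4 lists three sensitivity analyses of the primary endpoint. The first re-estimates the decline from good-quality home readings, "excluding measurements with a difference >50% or <50% from baseline site FVC". The second does so "excluding patients with measurements collected for less than 30 days after baseline". The third repeats both "by a single arm repeated measures mixed model with patient effects and day of measurement fitted as random effects", with the semi-annual mean FVC decline over the peri-diagnosis period as its stated target. Further models are optional: they "may be performed using a repeated measures mixed model by including additional factors and covariates (e.g. gender, height) into the model", and other covariance structures may be tried.

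The primary estimator is in Section 4.5.1. Each patient's readings are regressed on study day, and the decline is the "individual difference in predicted values between baseline (study day 0) and study day 183 from the linear regression", which equals the slope times 183. These values are averaged over IPF patients and shown "together with two-sided 95% confidence intervals based on percentiles of the t-distribution".

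For site measurements, Section 4.2.2 states: "Baseline is defined as the measurement collected at the enrollment visit of each assessment". Section 2.2.1 adds a plausibility screen: "FVC values outside a range from 400 ml to 6000 ml will also be excluded from analysis".

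**The concern.** Two things look wrong.

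**The model.** The mixed-model sentence names patient and day of measurement, both as random effects, and nothing else. A mean decline is normally the fixed coefficient of day. Without that term, the wording could be taken as patient and day entered as random classification factors, which gives only a mean FVC level. It could also be taken as a random slope centred on zero, which gives only predicted patient slopes shrunk towards zero. The optional covariates and covariance structures do not add the missing term. The 183-day rule in Section 4.5.1 is written for each patient's own regression line, so it does not say which mixed-model quantity is to be multiplied.

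**The exclusion.** Read literally, dropping readings that differ by more than 50% or by less than 50% drops almost everything.

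At stake would be a sensitivity result that disagrees with the primary one only because of how a sentence was programmed.

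**Working it through.** **1. The plan's own precision figure.** Inputs from Section 2.3: n = 72, SD = 70 mL, mean decline 50 mL.

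- Half-width = 1.96 × 70 / √72 = 16.17 mL, giving 33.83 to 66.17 mL as tabulated. (The text prints this half-width with a percent sign; the unit is mL.)
- With the t percentile on 71 degrees of freedom it is 16.45 mL, so the choice of percentile moves the limit by only 16.45 − 16.17 = 0.28 mL.

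**2. What the analyst needs and where it stands.**

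| Item | Source |
|---|---|
| Quantity to estimate | Semi-annual mean decline, stated in the third bullet |
| Coding of time | Study day as a continuous regressor, Section 4.5.1 |
| Time scale | 183 days, Section 4.5.1 |
| Interval | Two-sided 95%, Section 4.5.1 |
| Random terms | Patient and day, third bullet |
| Fixed day slope | Not written; implied by the quantity to estimate |

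Only the last row is open, and the first row settles it: a mean decline requires a mean slope.

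**3. What the three readings return.** Common inputs: 72 patients, patient slopes with mean −50 and SD 70 mL per 183 days. Assumed, not in the SAP: 80% of days recorded, between-patient SD of level 700 mL, and the noise and follow-up given below.

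*Fixed slope with random intercept and slope; decline = 183 × fixed slope.*
- Follow-up 30 to 540 days, day-to-day SD 50 / 100 / 200 mL, 300 data sets each: −49.6 / −49.4 / −50.6 mL.
- Follow-up 30 to 400 days, SD 100 / 200 / 300 mL, 30 data sets each: −49.7 / −47.8 / −48.5 mL, with standard errors 9.2 / 10.5 / 12.0 mL. The Monte Carlo errors are 9.2/√30 = 1.7, 10.5/√30 = 1.9 and 12.0/√30 = 2.2 mL, so all three agree with −50.

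*Patient and time as crossed random factors, fixed intercept only.* Fitted on weekly means (assumed baseline FVC 2800 mL), this gives a mean level of 2728 / 2745 / 2772 mL and no decline, so it does not perform the analysis the bullet orders.

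*Random slope with its mean held at zero.* The average predicted slope in the 30-to-400-day simulation is −39.7 / −30.7 / −25.7 mL. The estimated slope SD shows why. It rises from 67.7 / 67.5 / 69.7 mL with the fixed slope to 84.6 / 82.8 / 85.9 mL without it. Putting the mean decline into the variance predicts almost that:
- √(67.7² + 49.7²) = 84.0
- √(67.5² + 47.8²) = 82.7
- √(69.7² + 48.5²) = 84.9

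The mean decline has been pushed into the random-effect variance.

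The simulated 95% half-widths for the fixed-slope model at 30 to 540 days (17.0 to 19.3 mL) should not be set against 16.17 mL as a loss of precision. The SAP's 70 mL is the SD of the measured decline; the simulation uses it for true slopes and then adds reading noise.

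**4. The 50% exclusion.** The 400 to 6000 mL screen contains 6000 − 400 + 1 = 5601 whole-mL values. For an example baseline site FVC of 2800 mL, the printed rule keeps at most two of them (1400 and 4200 mL). Read as more than 50% above or below, it keeps 1400 to 4200 mL, which is 2801 values. The literal rule leaves no usable data and would be noticed at the first run.

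**The case for a change.** The strongest case for a change is that an SAP exists so that the estimator is not left to the programmer, and these analyses are committed outputs. The primary model is written as an equation; this one is a single clause. If someone took the clause literally with day as continuous, held the mean slope at zero and averaged the predicted slopes, the result would fall short of the fixed-slope result by 49.7 − 39.7 = 10.0, 47.8 − 30.7 = 17.1 or 48.5 − 25.7 = 22.8 mL. That is comparable with the planned half-width of 16.17 mL and could be misread as a lack of robustness.

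The arithmetic is sound, but the premise is not realistic. It needs an analyst who is told to estimate a mean decline, fixes that mean at zero, and then recovers a number by averaging shrunken predictions. Naming patient and day as random effects is common shorthand for random intercepts and slopes around a mean line.

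What stands is that the fixed slope is not written down, and that the 183-day rule has to be carried over from individual slopes to the fixed coefficient. The exclusion text also cannot be followed as printed, though a minus sign may simply have been lost, in the SAP or in reading the PDF.

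**Conclusion.** The concern does not call for a change. The missing fixed slope is a gap that analysts fill sensibly: the bullet's own target requires it, and Section 4.5.1 supplies the scale, the coding of day and the interval. Under that reading the simulated decline is 47.8 to 50.6 mL against a true 50 mL, so no bias arises. The 10 to 23 mL shortfall belongs to a model that contradicts the analysis's stated purpose. The 50% rule is a clerical slip whose meaning is plain, and correcting it would alter no analysis that would actually be run.

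The reach is also small: supportive re-estimates in a hypothesis-generating, descriptive study, with the per-patient primary estimator unaffected. The simulated figures depend on assumed noise, adherence, baseline FVC and follow-up. The conclusion itself rests on the wording of Sections 4.5.1 and 4.5.4 and on the analyst working to the quantity the bullet names.
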